9.4 PULSE Intervention

The PULSE intervention group will receive flexibility exercises, AROM for the upper and lower extremities, breathing exercises and TENS. During the AROM exercises, participants will be working to increase flexibility and range of motion in order to increase the motion the participant produces. The exercises will include the neck, shoulders, arms, trunk, hips, knees and ankles. During all of the AROM exercises, the participant will focus on deep breathing techniques. Progression will be gradual by beginning with three repetitions and slowly progressing to 10 reps. We will add a second set of exercises when necessary. This portion of the session will last approximately 20-30 minutes.

The second part of the session will use sensory level electrical stimulation to the lower extremity muscle groups. The TENS portion of intervention is intended to decrease pain and increase muscle recruitment thereby allowing greater ease of mobility. Conventional TENS uses low-level electrical current to stimulate superficial cutaneous nerve fibers through the skin. The amount of current for sensory level stimulation is the level which the participant detects as a "tingling" sensation and is not high enough to produce a visible muscle contraction (below motor threshold).⁵ To achieve sensory level stimulation, we will use a frequency of 80 pulses per second, pulse duration 50 μ sec, and amplitude which produces a comfortable paresthesia (tingling or 'pins and needles' sensation). Flexible carbonized, disposable electrodes coated with a self-adhesive conductive polymer will be applied to the skin. The electrodes will be placed bilaterally near the motor points on muscle bellies (the gluteal complex, the quadriceps, and the gastrocnemius) for seven minutes per muscle group. The muscle regions selected are important for function after hip fracture. Repetitions and duration of the AROM program, as well as TENS intensity will be recorded in the training log.

9.5 Treatment Fidelity Plan

Treatment fidelity^{151,152} will be evaluated with regard to: (1) design, which focuses on whether the interventions are consistent with underlying theories, and whether the study is free of contamination such as treatment crossover or unintended motivational interventions; (2) training, which addresses skill acquisition and maintenance in PTs; (3) delivery, or the assessment that the two interventions were implemented as intended; (4) receipt, which focuses on whether or not the participant understood and received the intervention as intended. Overall, treatment fidelity data will provide information on the adherence of the PTs to the interventions, and the adherence of the participants to the prescribed activities. Monitoring treatment fidelity also will provide an opportunity to address potential study problems, such as drift from the intervention protocols which could threaten the study's ability to detect treatment differences.

9.5.1 Initial Training for Procedural Reliability

The Intervention Monitor (IM) will train PTs in either PUSH intervention or PULSE intervention procedures. In order to minimize crossover, the PTs will only be trained on one intervention. There will be separate training sessions for each intervention and the PTs will not know the details of the other intervention.

Knowledge of procedures will be tested by written examination and by psychomotor skills observation via video. The IM will document that PTs are "CAP certified PTs" and provide a certificate of completion after they demonstrate competence on the written exam and video observation. PTs also need to bring evidence to the training session that they are currently

CPR certified. As new PTs join the study, training will be conducted on an individualized basis following the same procedures.

9.5.2 Ensuring Ongoing Competency

We will use a multi-faceted approach to ensure ongoing treatment fidelity. The approaches include direct observation of skills by the clinical site coordinators, mandatory monthly telephone calls with all active PTs, periodic review of PT log books, access to online discussion boards, and face-to-face meetings with the intervention team at least twice per year.

Direct Observation: Direct observations of PTs as they perform the interventions will be conducted by the clinical site coordinators who will be trained on both intervention protocols. The coordinators will document their observations using a structured checklist that addresses data completeness, physical performance, qualitative observations, and verbal and non-verbal communication. In the PUSH intervention group, the checklist will also document whether the participant completed the necessary repetitions at the appropriate intensity and whether the participant completed 20 minutes of aerobic exercise at the proper intensity. The checklist for the PULSE intervention group will document that the participants completed the AROM exercises, had electrodes placed appropriately, and received the TENS at the appropriate level and for the proper amount of time. There will be two observation visits during the PT's first assigned participant's 16-week intervention period and then one observation per quarter for PTs who have conducted a complete 16-week intervention period for at least one participant. If the total score on the checklist is less than 90%, the IM and clinical site PI will be notified. A remediation plan will be proposed that will offer refresher training to ensure accurate understanding of the protocol, follow-up observation visits, and possible dismissal if warranted.

Mandatory Conference Calls with PTs: The IM will conduct monthly telephone calls with the PTs who are currently active with participants. The Treatment Fidelity Manager will take minutes of the telephone meetings to document ongoing training. During these calls (which will be done separately for the PTs in the two groups), the IM will ask questions to identify problems with delivering the intervention. If problems are identified, the IM will schedule an individual telephone call and review of PT log books. Additional follow-up will be mandated if there are modifications to the exercise prescription that are due to PT factors. A remediation plan will be followed if there is ongoing lack of progress.

Periodic Review of Intervention Logs: Clinical site coordinators will review PT intervention logs when the PTs come to the study office to pick up study medications or to submit completed forms. The coordinator will note if PTs are completing logs and if there are modifications to the intervention protocols. This information will be sent to the IM for discussion during the monthly phone calls.

IM Site Visits: The IM will visit each site semi-annually to meet with all the PTs, with separate meetings for each intervention group. This will be a team building visit emphasizing proper delivery of the intervention and discussing issues specific to the site.

9.5.3 Monitoring Physiologic Response

As a measure of treatment fidelity, we will monitor physiologic response (heart rate) during the intervention sessions using Polar heart rate monitors. The monitors will be worn by all participants at all intervention sessions. The Polar monitor allows the operator to indicate the start and end of distinct time segments referred to as "laps" by the device's software system. Each intervention session will consist of four laps, defined as follows:

Lap	PUSH Intervention	PULSE Intervention
1	Greeting, health questions, BP, HR	Greeting, health questions, BP, HR
2	Strength training, BP, HR	AROM training, BP, HR
3	Endurance training	TENS
4	Wrap-up	Wrap-up

BP=blood pressure; HR=heart rate; AROM=active range of motion; TENS=transcutaneous electrical nerve stimulation.

The Polar monitoring will provide a dichotomous variable reflecting whether, during laps 2 and 3 of each intervention session, the participant's average HR was equal to or greater than his or her target heart rate (± 5 beats). The target heart rate is defined as 50% of heart rate reserve and is calculated as follows:

Target HR= $((220-\text{age}) - \text{RHR}) * 0.5 + \text{RHR}$, where RHR=resting heart rate.

In addition, the IM will perform ongoing qualitative reviews of the HR curves that are generated by the software. She will examine the duration of the laps as well as the pattern of activity within the laps (height of curve, duration of the rise in HR, number of times HR rises within a lap) and compare them to pre-specified criteria established for each intervention. If the pattern of HR curves deviates from the pre-established expectations, she will confer with the PT regarding the possible reasons and implement appropriate actions as necessary.

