HR will be measured by palpation of the radial artery recorded every five minutes and it will be averaged over 20 minutes of continuous exercise. The PT will calculate the HR training zone based on the heart rate reserve (HRR) method (HR max-HR rest) multiplied by 50% and then added to HR rest. HR max will be calculated as 220 minus the participant’s age. This prescription is consistent with moderate intensity exercise and has been shown to increase aerobic capacity in elders.¹⁴⁷⁻¹⁴⁹ If the person is taking medication that controls heart rate (e.g., beta-blockers), Borg’s Rating of Perceived Exertion (RPE) scale will be used.¹⁵⁰ The training intensity using the RPE scale will be “moderate” work as consistent with a 3-5 on the 0-10 scale.

The endurance intervention will begin initially with two to three minutes of continuous upper and lower extremity AROM with the participant sitting. These exercises are intended to increase the participants’ HR or exertion closer to the target zone. The participant will then be asked to walk on level surfaces and up and down one or more steps, if able and available, to keep the HR within the training zone for 20 minutes. The PT can also engage the participant in additional exercises such as upper and lower extremity AROM exercises to keep the HR elevated. The

target HR will be 30% of HRR in the first week of the program, 40% of HRR in the second week, and 50% of HRR in weeks 3 through 16.

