9.6 Scheduling Intervention Visits

There are three requirements for scheduling of intervention visits:

1. The first intervention visit should occur on Day 7 or earlier, where the day of randomization = Day 0.
2. The schedule of intervention visits is anchored to the date of randomization regardless of when the intervention starts.
3. Intervention visits should never occur on two consecutive days, even when moving from one week to the next.

For all randomized participants, Week 1 will begin on the day of the first intervention visit or on Day 7 post-randomization, whichever is earlier. Subsequent weeks will start on the same day of the week as Week 1. For example, if the participant's first intervention visit is on a Wednesday, each intervention week for that participant will extend from Wednesday to Tuesday (inclusively). Alternatively, if the first visit has not yet occurred by Day 7 and Day 7 is a Monday, then the participant's intervention weeks will extend from Monday to Sunday (inclusively).

In certain circumstances (e.g., illness, travel), the first intervention visit may be scheduled after Day 7.

Ideally participants will receive 2 visits per week for 16 weeks post-randomization (32 visits total). However, missed visits in a given week can be replaced by makeup visits in subsequent weeks (not to exceed 3 visits in any given week) as long as the visits are on non-consecutive days. If the participant has not had 32 visits by the end of 16 weeks, makeup visits can be performed during the subsequent two weeks to get as close as possible to the target of 32 visits.

Section 10: Study Measures

A list of study measures is provided below. All of the measures will be interview-based or based on observations of performance or physiological assessments. No proxy data will be allowed at baseline. However, at the 16-week follow-up visit, a proxy may be contacted to provide information about the participant's walking ability. This information will be used as part of the adjudication process, as described in section 11.5. Also, the four-week phone calls will be conducted with a proxy when the participant is not available.

In the description of measures below, we identify the measures that will not be collected for participants consented under protocol version 11.0 or later.

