10.6 Other Measures to be Monitored

10.6.1 Adherence

Adherence with PT interventions. PTs will submit a visit form for each of the 32 visits that records date of visit; start and end time of the visit; reason for missed visit; what activities were performed; and whether activities were performed as prescribed. For the PUSH group, we will also obtain information about the intensity of each activity at initiation of the intervention and every four weeks during the intervention period. Logs completed by PTs will record the detail of each designated activity during intervention sessions as well as any precautions or modifications to activities. Reasons for protocol variations will be noted in the PT log books.

Additionally, at the end of each intervention visit, the PT will retrieve the average HRs for laps 2 and 3 from the Polar heart rate monitor receiver and record them in the logbook and on the appropriate data forms. The Polar heart rate monitoring will provide a dichotomous variable reflecting whether, during laps 2 and 3 of each intervention session, the participant's average HR was equal to or greater than his or her target heart rate (± 5 beats). In addition, the IM will perform ongoing qualitative reviews of the HR curves to ensure that the pattern of activity is consistent with pre-specified criteria established for each intervention.

Adherence with study vitamins/supplements. Vitamin D, calcium, and multivitamin adherence will be monitored by pill counts every four weeks during the intervention period and by self-report during the 4-week telephone calls for the entire 16-week study period.

In protocol version 11.0, we will eliminate the collection of information on use of study-provided dietary supplements. However, procedures for drug accountability will remain unchanged (see section 3.2.3).

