Fall	
 1. If there is bleeding/wound, apply pressure using emergency kit for wound; call 911 if needed. If participant is unable to stand or move the injured part, call 911 and keep them warm and comfortable. 2. Report all falls to clinical site coordinator. 3. Complete an incident report.
Stroke symptoms	Call 911 immediately.

ALERT	ACTION
Dizziness during exercise	
 1. Stop exercise and have person sit or lie down. 2. If sitting is not sufficient to resolve dizziness, then check vital signs. 3. Call 911 if clinically unstable. 4. Report to PCP if heart rate is less than 60 (and not usually so), the dizziness is new in onset; or if the BP is > 160/100 or systolic <90. 5. Report event to clinical site coordinator and study clinician.
Resting pulse Rate > 120 or < 40 beats/min	
 1. PT will stop delivery of the intervention. 2. Qualified staff will consult with the study clinician and follow up as needed. 3. PT will resume delivery of the intervention only after the participant receives medical clearance.
New irregular heart rate with complaint of heart palpitations	
 1. Do not exercise and call PCP. 2. Report to clinical site coordinator and study clinician for follow-up. 3. Wait for medical clearance to resume exercise.
New acute musculoskeletal pain during exercise (pain > 5 on VAS)	
 1. Have the participant stop the exercise and rest. 2. Attempt to alter position of participant to reduce pain. If pain persists, do not continue specific exercise. Attempt to do other exercises. 3. If pain does not resolve, refer to PCP or orthopedist and study clinician.
New, acute, non-musculoskeletal pain (pain > 5 on VAS)	
 1. Do not exercise. 2. Take pain history and call PCP. 3. Report to clinical site coordinator and study clinician for follow-up and clearance.
Acute change in mental status	
 1. Do not exercise. 2. Call PCP or if unavailable, call 911. 3. Report to clinical site coordinator and study clinician for follow-up and clearance.
Participant expresses desire to commit suicide	
 1. Call PCP and report findings. 2. Report to clinical site coordinator and study clinician for follow-up and clearance.

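### The heart-rate fidelity indicator holds PUSH lap 3 to 50% of heart rate reserve in every session, although the endurance prescription is 30% in week 1 and 40% in week 2

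*Protocol*

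**What the plan says.** Protocol 9.5.3 has all participants wear a heart-rate monitor at all intervention sessions and presents the result as a fidelity measure. Each session has four laps. In PUSH, lap 2 is strength training and lap 3 is endurance training; in PULSE they are range-of-motion exercise and TENS. The indicator asks whether the average rate reached the participant's own target, within 5 beats. That target is a single figure: "The target heart rate is defined as 50% of heart rate reserve and is calculated as follows", followed by the formula ((220 − age) − RHR) × 0.5 + RHR, where RHR is resting heart rate.

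Protocol 10.6.1 repeats the indicator under adherence with the PT interventions: "The Polar heart rate monitoring will provide a dichotomous variable reflecting whether, during laps 2 and 3 of each intervention session", the target was reached. It also says that "the PT will retrieve the average HRs for laps 2 and 3 from the Polar heart rate monitor receiver" and records them on the data forms.

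Protocol 9.3 sets a ramp for PUSH endurance work: the "target HR will be 30% of HRR in the first week of the program, 40% of HRR in the second week", then 50% in weeks 3 to 16. The same section uses Borg's perceived-exertion scale (RPE) in place of heart rate for people on rate-controlling drugs.

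The SAP does not mention the indicator.

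**The concern.** A fidelity indicator should show whether the prescribed treatment was delivered. Here the prescription for PUSH lap 3 changes over the first two weeks and the yardstick does not. A therapist who follows the ramp exactly can be recorded as having missed the target, while one who overshoots it can be recorded as having met it.

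What is at stake is the description of dose. Protocol 5.2 attributes earlier null results to inadequate exercise dose, so readers will look closely at the heart-rate data. Early sessions delivered as intended could be read as under-dosed.

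**Working it through.** **Inputs.** HRR = 220 − age − RHR (9.3 and 9.5.3). Fidelity target: RHR + 0.5 × HRR (9.5.3). Tolerance: 5 beats (9.5.3). Prescribed fraction f: 0.3 in week 1, 0.4 in week 2, 0.5 from week 3 (9.3). Visits: 2 per week, 32 in total (9.6). The documents give no resting rates, so those below are assumptions. They also give no worked value of the target, so there is no stated figure to reproduce.

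**Pass mark.** Reading the tolerance in the most lenient way, mark = RHR + 0.5 × HRR − 5.

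**Condition for a miss.** A lap 3 average exactly at prescription is RHR + f × HRR. It is below the mark when (0.5 − f) × HRR > 5.

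- Week 1: 0.2 × HRR > 5, so HRR > 25. It reaches the mark only if age + RHR ≥ 220 − 25 = 195.
- Week 2: 0.1 × HRR > 5, so HRR > 50. It reaches the mark only if age + RHR ≥ 220 − 50 = 170.

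If the tolerance does not lower the bar, every exact lap 3 in weeks 1 and 2 is below target.

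**Examples (assumed age and RHR, bpm).**

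| Age, RHR | HRR | 50% target | Mark | Week 1 prescribed | Week 2 prescribed |
|---|---|---|---|---|---|
| 60, 60 | 100 | 110 | 105 | 90 (15 short) | 100 (5 short) |
| 80, 70 | 70 | 105 | 100 | 91 (9 short) | 98 (2 short) |
| 90, 90 | 40 | 110 | 105 | 102 (3 short) | 106 (passes by 1) |

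Over a grid of ages 60 to 95 in steps of 5 and RHR 60, 70, 80 and 90 (32 combinations), an exact lap 3 misses in all 32 in week 1 and in 26 of 32 in week 2. The grid shows the range; it is not an estimate of frequency.

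**Visits exposed.** Current schedule: 2 weeks × 2 visits = 4 of 32 = 12.5%. Participants treated before the late-2014 change had three visits per week for the first eight weeks and 40 visits in all. For them it would be 2 × 3 = 6 of 40 = 15% if the same ramp applied, which the documents do not state.

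**Session-level variable (current schedule).** The rule for combining laps 2 and 3 is not given.

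- If both laps must reach target, an exact lap 3 alone fails 4 of 32 visits when HRR > 50, 2 of 32 (6.25%) when HRR is above 25 and up to 50, and none when HRR ≤ 25.
- If the laps are averaged or either suffices, lap 3 causes between 0 and 4 failures, depending on lap 2. With equal-length laps averaged (assumed) at age 80 and RHR 70, lap 2 would need 2 × 100 − 91 = 109 bpm in week 1, or 2 × 100 − 98 = 102 bpm in week 2.

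**After the fix.** With week-specific targets, the age 80, RHR 70 participant has targets of 91, 98 and 105 bpm, and an exact lap 3 meets its target in every week.

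**The case against.** The best defence is that 50% of HRR is a common physiologic benchmark. Section 9.3 itself defines the general training zone at 50%, with 30% and 40% as a two-week lead-in. The indicator also covers PULSE laps and PUSH strength work, which have no heart-rate prescription, so for those laps it can only be descriptive. On that reading, a low value in week 1 is simply correct. This stands for PUSH lap 2 and for PULSE. It does not settle PUSH lap 3: 9.5.3 calls the variable a fidelity measure against the participant's target, and 9.3 gives that lap a different target in those weeks. The intervention-specific criteria mentioned in 9.5.3 belong to the separate qualitative review of heart-rate curves and leave the yes/no rule unchanged.

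It is also fair to say that nothing is lost, since lap averages and visit dates are recorded and a week-specific version can be derived later. That makes the repair cheap; the rule as written still misdescribes these sessions.

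Three stronger readings are tempting, and the documents do not support them.

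- *That the efficacy results are affected.* Protocol 15.4 defines adherence by visits completed, and the SAP dropped the nonadherence analysis.
- *That therapists would be wrongly remediated.* No text ties the indicator to remediation. Intensity is also checked by palpated heart rate, the observation checklist, visit forms and the curve review.
- *That nobody under 75 could ever reach the week 1 mark.* At age 74 this needs a resting rate of at least 195 − 74 = 121. Table 3 (Protocol 12.1.5) says of a resting pulse above 120 that the "PT will stop delivery of the intervention", but it allows delivery to resume after medical clearance, so the bar is not absolute.

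**Conclusion.** The inconsistency is real and small. As written, the indicator puts an exactly delivered PUSH lap 3 below target in week 1 when HRR > 25 bpm and in week 2 when HRR > 50 bpm. It exposes up to 4 of 32 PUSH visits on the current schedule. It does not follow that 12.5% of sessions will be misrecorded: lap 3 may run above the early targets, the age and resting-rate mix is not given, and the lap-combination rule is open. The result assumes the lenient reading of the 5-beat tolerance and a lap average exactly at prescription. The consequence is confined to descriptive fidelity reporting. This is a worthwhile tidy-up and poses no threat to the trial's conclusions.

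**What to change.** Score PUSH lap 3 separately against the week-specific target in 9.3 (30%, 40%, then 50% of HRR) with the same 5-beat tolerance, using the lap averages and visit dates already recorded. Keep the 50% figure for PUSH lap 2 and for PULSE sessions, labelled as a common descriptive benchmark only. Report participants guided by RPE as not evaluable by heart rate where they can be identified, and note the limitation where they cannot.

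The derivation note should also settle three missing details:

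- How laps 2 and 3 combine, if a session-level variable is kept.
- Which week numbering applies when the first visit falls after Day 7. Section 9.6 largely answers this, since "The schedule of intervention visits is anchored to the date of randomization regardless of when the intervention starts".
- Whether lap 3 includes the seated warm-up of two to three minutes. In a worst case of 3 minutes at resting rate and 20 minutes at target, age 60 and RHR 60 in weeks 3 to 16 gives (3 × 60 + 20 × 110) / 23 = 103.5, below the mark of 105. Age 80 and RHR 70 gives (3 × 70 + 20 × 105) / 23 = 100.4, above the mark of 100.

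The cost is a little more derivation work and a slightly smaller heart-rate denominator. No new data are needed and no training intensity changes.
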